3.6 CONCURRENT THERAPIES

Other cancer chemotherapy, radiation, immunotherapy, biologic therapy, or investigational agents cannot be administered to patient while receiving mithramycin.

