3.7.2 Criteria for removal from Study

- 1. Death
- 2. Lost to follow-up
- 3. Withdrawal of consent for any further data submission
- 4. Entry onto another therapeutic study
- 5. Patients who are taken off treatment for toxicity will be followed until resolution of toxicity and then taken off study (at least 30 days after the last dose of mithramycin).
- 6. The PI deems it is in the best interest of the patient

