c. Evaluation of Best Overall Response

The best overall response is the best response recorded from the start of the treatment until disease progression/recurrence (taking as reference for progressive disease the smallest measurements recorded since the treatment started). The patient's best

response assignment will depend on the achievement of both measurement and confirmation criteria.

Target Lesions	Non-Target Lesions	New Lesions	Overall Response	Best Overall Response when Confirmation is Required*
CR	CR	No	CR	≥ 4 wks. Confirmation**
CR	Non-CR Non-PD	No	PR	≥ 4 wks. Confirmation**
CR	Not evaluated	No	PR	
PR	Non-CR Non-PD Not evaluated	No	PR	
SD	Non-CR Non-PD Not evaluated	No	SD	Documented at least once ≥ 4 wks. from baseline**
PD	Any	Yes or No	PD	No prior SD, PR or CR
Any	PD***	Yes or No	PD	
Any	Any	Yes	PD	

*See RECIST 1.1 manuscript for further details on what is evidence of a new lesion.
**Only for non-randomized trials with response as primary endpoint.
***In exceptional circumstances, unequivocal progression in non-target lesions may be accepted as disease progression

- d. Patients with a global deterioration of health status requiring discontinuation of treatment without objective evidence of disease progression at that time should be reported as “*symptomatic deterioration*.” Every effort should be made to document the objective progression even after discontinuation of treatment.
- e. In some circumstances, it may be difficult to distinguish residual disease from normal tissue. When the evaluation of complete response depends on this determination, it is recommended that the residual lesions be investigated (fine needle aspirate/biopsy) before confirming the complete response status.

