8.2.1 Methods of Analysis

Patients who are considered evaluable for response will be included in an analysis of time to progression. Time to progression will be estimated using the product-limit method of Kaplan and Meier. The probability of progression free survival at 6 months will be summarized. Response rates will be calculated as the percent of patients whose best response is a CR or PR, and the fraction of responses obtained will have a 95% confidence interval, which takes into consideration the two-stage nature of the design (50). Toxicity information recorded will include the type,

severity, time of onset, time of resolution, and the probable association with the study regimen. Tables will be constructed to summarize the observed incidence by severity and type of toxicity.

Time to progression will be taken as the number of days from enrollment until: (1) disease progression; (2) death because of treatment complications; (3) resection of measurable tumor; or (4) last patient follow-up whichever is first. Patients will be considered to have experienced a progression event if (1) or (2) occurs. Otherwise, the patient will be considered censored for time to progression.

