8.3 EVALUATION OF RESPONSE

Any patient who is enrolled and receives at least one dose of mithramycin will be considered evaluable for response provided: (1) the patient demonstrates progressive disease or death while on protocol therapy; (2) the patient is observed on protocol therapy for at least one cycle and the tumor is not removed surgically prior to the time complete response or partial response is confirmed; or (3) the patient demonstrates a complete or partial response as confirmed according to protocol criteria. Patients who electively terminate therapy before receiving all 7 doses of mithramycin during the first treatment cycle and do not expire within 28 days from start of treatment will be replaced. Patients who demonstrate a complete or partial response will be considered to have experienced a response. The evaluation period for determination of the best response will be 6 treatment cycles. All other patients will be considered non-responders.

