^c1 mL of plasma will be obtained, filtered through a 0.22 micron filter, frozen and saved by hematology pathology for future reference if needed, prior to receiving drug on day 1 of cycle 1 and 2 only. See **Error! Reference source not found.** for details.

^dCoagulation studies: drawn on days 1, (3, 4 or 5) and (7, 8 or 9) or as clinically indicated. If screening coagulation studies drawn within 1 week of starting drug, day 1 can be omitted for cycle 1 only.

^eExcluded by history only. No laboratory testing of HIV, HBV or HCV is required.

^frequired at screening/prior to cycle 1 and prior to each subsequent cycle on females of childbearing potential

^grequired at screening/prior to cycle 1 and prior to each subsequent cycle

^gperformed after every EVEN numbered treatment cycle, i.e. cycle 2, cycle 4, etc until off therapy and then every two months until off study or as indicated by clinical response criteria see (section 6.2). Imaging studies will be sent to NCI POB for volumetric analysis (see **Error! Reference source not found.** for details).

^hPK samples: prior to and at the completion of the first infusion, then trough and end of infusion samples with day 4 and 7 doses, and 24 and 48 hours after day 7 dose. Samples will therefore be drawn on days 1, 2, 4, 7, 8, 9 as indicated in **Error! Reference source not found.** and **Error! Reference source not found..**

ⁱA serum sample for potential biomarker analysis will be obtained prior to the first mithramycin injection, and then at the time of each restaging studies. See **Error! Reference source not found.** for details.

^jEligibility and timing for mandatory biopsy is defined in **Error! Reference source not found..**

^kSee **Error! Reference source not found.** to obtain sheet to record adverse events at home

^lSee **Error! Reference source not found.** to record all medications taken at home

^mPost therapy evaluations will be completed until at least 30 days after the last dose of mithramycin and until resolution of toxicity.

ⁿAll EKGs should be done prior to infusion. EKG on day 4 to be done on cycle 1 only.

^o2.5 mg dexamethasone/m² BSA PO or IV starting 12 hours before the first dose of mithramycin, then prior to the first dose, and then twice daily for 24 hours after the last dose of mithramycin

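### Resection is the only treatment change that censors time to progression; off-trial chemotherapy or radiotherapy started without progression leaves the clock running for patients still followed

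*Combined protocol and SAP*

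**What the plan says.** Section 8.2.1 measures TTP from enrollment to the first of four end points: (1) progression, (2) death from treatment complications, and then "3) resection of measurable tumor; or (4) last patient follow-up whichever is first". It then separates events from censoring: "Patients will be considered to have experienced a progression event if (1) or (2) occurs"; everything else is censored. The curve is a Kaplan-Meier estimate in response-evaluable patients, and the 6-month probability is to be summarized. Section 1.1.2.4 lists TTP as a secondary objective, to be defined preliminarily.

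Four other places decide what can happen after mithramycin stops:

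- Section 3.6: other anti-cancer treatment "cannot be administered to patient while receiving mithramycin". The bar ends with the drug.
- Section 3.7.1: protocol therapy can end without progression, for example by refusal, in the patient's best interest, for a concurrent serious illness, or for toxicity.
- Section 3.7.2: the off-study criteria include "Entry onto another therapeutic study" and, for patients stopped for toxicity, its resolution (at least 30 days after the last dose). Starting treatment outside a trial is not listed.
- Appendix 3, footnote g: imaging after every even cycle "until off therapy and then every two months until off study", or as indicated by response criteria.

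**The concern.** Take a patient who declines further mithramycin while stable, starts commercial chemotherapy and remains on study with scans. No rule in 8.2.1 stops the clock. If the new treatment holds the disease, that time counts as progression-free time in the mithramycin curve. If the disease progresses on the new treatment while the patient is followed, an event is recorded at that later date and charged to mithramycin.

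The plan already accepts the principle that a treatment change can make later follow-up uninformative, since it censors at resection. Radiotherapy to the same lesion raises the same difficulty and is treated differently. At stake is the interpretation of a descriptive 6-month figure from at most 24 evaluable patients, where a few cases can be visible. Without a written rule, their handling would be settled after the data are known.

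**Working it through.** **Plan figure.** The documents state no median, rate, power or sample size for TTP, so there is nothing to reproduce. The two-stage response design is a separate matter: its stated 63% early-termination probability is 0.95^9 = 0.630, and TTP plays no part in it.

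**Who is exposed.** Setting 8.2.1 beside 3.6, 3.7 and Appendix 3:

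| After stopping without progression | What ends the TTP clock before progression |
|---|---|
| Resection | Item (3), censored |
| Entry onto another therapeutic study | Off study (3.7.2), censored through item (4) |
| Stopped for toxicity, toxicity resolves | Off study, at least 30 days after last dose, censored through item (4) |
| Stopped for toxicity, unresolved; commercial therapy starts | Nothing while follow-up continues |
| Refusal, best-interest withdrawal or concurrent illness; commercial therapy starts; still on study | Nothing while follow-up continues |

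Only the last two rows are open.

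**Size per patient.** The comparison that matters is with the proposed handling, which is censoring.

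- From the plan: 24 evaluable patients (8.2) and a 6-month landmark (8.2.1).
- Assumed, not in the documents: exponential TTP with median m of 2 to 4 months; switch at month 2; the new therapy holds the disease; follow-up runs past month 6.

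A patient counted as progression-free at month 6 contributes 1/24 to the estimate. Censored at time t, that patient's weight passes to those still at risk, and the expected contribution is (1/24) x S(6)/S(t). The difference is

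(1/24) x [1 - S(6)/S(2)], with S(6)/S(2) = 0.5^(4/m).

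- m = 2: (1 - 0.250)/24 = 3.1 points
- m = 3: (1 - 0.397)/24 = 2.5 points
- m = 4: (1 - 0.500)/24 = 2.1 points

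If follow-up instead ends one month after the switch, the difference is (1/24) x [S(6)/S(3) - S(6)/S(2)]:

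- m = 2: (0.354 - 0.250)/24 = 0.4 points
- m = 3: (0.500 - 0.397)/24 = 0.4 points
- m = 4: (0.595 - 0.500)/24 = 0.4 points

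**Check by simulation.** Kaplan-Meier with 24 patients and 3,000 replicates; mean 6-month estimate under the same assumptions:

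| Median (months) | Switchers of 24 | Censored at switch | Followed past month 6 | Off study one month after switch |
|---|---|---|---|---|
| 2 | 2 | 0.123 | 0.186 | 0.132 |
| 2 | 6 | 0.128 | 0.313 | 0.156 |
| 3 | 2 | 0.249 | 0.300 | 0.258 |
| 3 | 6 | 0.252 | 0.402 | 0.278 |
| 4 | 2 | 0.354 | 0.395 | 0.362 |
| 4 | 6 | 0.355 | 0.479 | 0.378 |

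With continued follow-up the total shift runs from 0.395 - 0.354 = 4.1 points (2 switchers, median 4) to 0.313 - 0.128 = 18.5 points (6 switchers, median 2). Per switcher that is 4.1/2 = 2.1 to 18.5/6 = 3.1 points, in line with the formula. With follow-up ending a month after the switch, the total shift is about 1 to 3 points.

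**The case against.** The best defense is that follow-up after treatment is meant to be short. Section 3.5.2 monitors patients until toxicity recovers or stabilizes, and footnote m of the study calendar runs post-therapy evaluations until at least 30 days after the last dose and until toxicity resolves. Many patients would leave before or around the first two-monthly scan and be censored through item (4). This stands, and it narrows the exposed group considerably. It does not close the gap: footnote g keeps imaging going until off study, and 3.7.2 has no criterion that takes a patient off study for starting commercial therapy.

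It is also fair that TTP has no test or threshold, that the direction is conditional because later therapy may fail, and that censoring at a switch can itself be informative. All three stand. They limit the importance of the point and shape the remedy.

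A reader might go further and infer that the response decision is exposed too. Item (3) of 8.3 admits a patient when "the patient demonstrates a complete or partial response as confirmed according to protocol criteria", without tying this to protocol therapy, and 6.2.1.1 says "The best overall response is the best response recorded from the start of the treatment until disease progression/recurrence". One response gained under another drug would move 2/24 to 3/24. The documents do not support resting the point on this. Section 8.3 confines best response to 6 treatment cycles, 8.2 examines the response of disease to mithramycin, and item (3) of 8.3 is an evaluability criterion, not the definition of response. Together these largely close that route.

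**Conclusion.** The gap in the TTP rule is real and limited. Non-protocol therapy outside a trial, started without progression, neither censors nor counts as an event, while resection censors. The effect on the 6-month figure is upward when the later therapy holds the disease; a later progression on that therapy is charged to mithramycin, so the direction is not fixed by the text.

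The documents give no rate of stopping without progression, so the total bias cannot be determined from them. Under the stated assumptions it is about 2 to 3 points for each such patient followed past month 6, and about 0.4 points if follow-up ends a month after the switch. A reader might infer 1/24 = 4.2 points per patient. That compares a progression-free patient with one counted as having progressed; against censoring it is too large.

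Nor does it follow that resection is the only route to censoring, because last follow-up also censors. The point concerns a secondary, preliminary endpoint and is worth making because the correction is cheap.

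**What to change.** In 8.2.1, reword item (3) to: resection of measurable tumor, or start of any non-protocol anti-cancer treatment (systemic, radiotherapy or surgery). State that such patients are censored at the last disease assessment before that treatment. Record its start date and type while the patient is on study.

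Because censoring at a switch may be informative, add two sensitivity analyses: (a) ignore the switch and use all follow-up, and (b) count the switch as an event.

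The cost is one clause in an amendment, a date and type field, and two extra Kaplan-Meier runs. The study calendar already marks concomitant medications in the post-therapy column, so the added collection is small. A few patients will be censored earlier, which the sensitivity analyses put in view. The response criteria and the two-stage rule need no change on this account.

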1.1.2 Secondary Objectives

- 1.1.2.1 Describe pharmacokinetic parameters for each dose level using non-compartmental methods (phase I and II)
- 1.1.2.2 Evaluate NR0B1 expression in patients with Ewing sarcoma using immunohistochemistry on archival tumor tissue, if available (phase I and II)
- 1.1.2.3 To prospectively evaluate the feasibility and utility of volumetric analysis of target lesions, and descriptively compare volumetric measurements to 1D (RECIST), and 2D (WHO) measurements (phase I and II).
- 1.1.2.4 Define preliminarily time to progression (TTP) in patients with Ewing sarcoma (phase II)

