After completion of therapy, patients will be monitored until recovered from toxicity to baseline or stabilized.

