3.5.3.3 Laboratory evaluation: CBC, Acute, Hepatic and Mineral panels, uric acid, LDH, PT/PTT

The patient may have evaluations and lab work obtained through his or her local physician between cycles or during follow up.

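### Time to progression is censored at last follow-up instead of the last disease assessment, so unscanned follow-up, where it occurs, can raise the 6-month estimate by a few points

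*Combined protocol and SAP*

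**What the plan says.** Section 8.2.1 measures time to progression from enrollment to the earliest of four dates: progression, death from treatment complications, "3) resection of measurable tumor; or (4) last patient follow-up whichever is first". On events it says: "Patients will be considered to have experienced a progression event if (1) or (2) occurs". Everyone else is censored. The estimator is named: "Time to progression will be estimated using the product-limit method of Kaplan and Meier". One summary figure is promised: "The probability of progression free survival at 6 months will be summarized". Last follow-up is not defined, and the last tumor assessment is not mentioned. Section 1.1.2 makes this a secondary, preliminary objective of phase II.

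Imaging is described in several places:

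- Section 3.5.1.5 has disease evaluated after every even cycle and, where feasible, at removal from treatment.
- Appendix 3, note g, continues imaging "until off therapy and then every two months until off study", with clinical response criteria as an alternative trigger. The calendar's radiology row is marked under post-therapy follow-up.
- Section 3.5.2 says that after therapy "patients will be monitored until recovered from toxicity to baseline or stabilized". It lists examination and laboratory tests. Section 3.5.3 adds an EKG. Neither lists imaging.
- Section 3.5.3 adds: "The patient may have evaluations and lab work obtained through his or her local physician between cycles or during follow up".
- Section 3.7.2, item 5, takes patients stopped for toxicity off study once it resolves, no sooner than 30 days after the last dose.
- Section 8.3, item (2), makes a patient evaluable for response, and so for time to progression, after one cycle on therapy.

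**The concern.** Progression under Section 6.2 is mostly a finding on scans: sums of diameters, new lesions, bone scan. A patient who has left treatment without progression and is then only examined has little chance of having an event recorded. Censoring at last follow-up nevertheless keeps that patient in the Kaplan-Meier risk set. Each such patient enlarges the denominator when other patients progress, which raises the curve. The 6-month probability is the one time-to-event figure that the plan promises, and this is a single-arm study with no control arm in which the same bias could cancel.

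**Working it through.** **1. Figure to reproduce.** The documents give no expected 6-month probability, event count or power for time to progression. The Simon design does reproduce on early termination: 0.95^9 = 0.630, against the stated 63%. It counts responses, so the censoring date does not enter it.

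**2. Where unscanned time can arise within the plan.**

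- Cycles last 28 days, so the first scheduled scan falls at about day 2 × 28 = 56. A patient is evaluable after one cycle (day 28) and may stop with no post-baseline scan if the removal scan is not feasible.
- Off study can come 30 days after the last dose, while note g's first post-therapy scan is due at about two months.
- Unscanned time matters only if it runs past another patient's event. Someone whose last dose is day 7 of cycle 1 and who is followed for 30 days is censored at day 37. That is before day 56 and has no effect on events found at scheduled scans. If toxicity takes beyond day 56 to resolve, the patient sits in the risk set at the first round of scans.

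**3. Direction.** At an event time with d events, n properly assessed patients at risk and u unscanned patients still counted, the Kaplan-Meier factor is 1 − d/(n + u) instead of 1 − d/n. It is larger whenever u > 0, so with the same events later censoring can only leave the estimate unchanged or raise it.

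**4. Size.** Simulation of 600 trials per setting. From the documents: 24 patients and scans every 8 weeks. Section 7.2.4 does not treat evaluations within 7 days of schedule as deviations, which supports letting scan dates vary by one week. Assumed, because the documents give no values: median time to progression of 8, 13 or 26 weeks, and 10% to 40% of patients leaving therapy without progression at a uniform time in weeks 4 to 26. The reference is the same analysis with every scan done.

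The last scheduled scan before week 26 is at week 24. With exponential times the reference should therefore be 2^(−24/13) = 27.8% for a 13-week median. The simulated references in the table are 27.1% to 28.1%.

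Kaplan-Meier estimate at 26 weeks (%), median 13 weeks, scan dates varying by one week:

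| Leave without progression | After leaving | Reference | Last follow-up | Last scan | Last follow-up − reference | Last scan − reference |
|---|---|---|---|---|---|---|
| 20% | schedule kept | 28.1 | 28.2 | 27.0 | +0.1 | −1.1 |
| 20% | 30 days unscanned | 28.1 | 30.3 | 27.3 | +2.2 | −0.8 |
| 20% | unscanned past 6 months | 28.0 | 34.4 | 26.7 | +6.4 | −1.3 |
| 40% | schedule kept | 27.1 | 26.9 | 24.3 | −0.2 | −2.8 |
| 40% | 30 days unscanned | 27.7 | 31.9 | 25.4 | +4.2 | −2.3 |
| 40% | unscanned past 6 months | 27.6 | 40.6 | 25.1 | +13.0 | −2.5 |

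Difference between the two rules (last follow-up minus last scan) over all settings:

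- schedule kept: 0.0 points with scans exactly on time, +0.3 to +2.6 with dates varying; last-follow-up censoring stays within about 0.6 points of the reference;
- 30-day unscanned tail: +0.8 to +6.4 points;
- unscanned past 6 months: +2.2 to +15.9 points.

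Part of each gap is last-scan censoring running low. Against the reference, with medians of 13 and 26 weeks, last-follow-up censoring is 0.6 to 4.2 points high with the 30-day tail. Last-scan censoring is up to 2.9 points low.

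**5. Against the trial's precision.** At 27% with 24 patients and no other censoring, the standard error is √(0.27 × 0.73 / 24) = 0.091, about 9 points.

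**The case against.** The strongest reply is that the plan does require scans. They are due at removal when feasible and every two months until off study, and Section 6.2.1.1 asks for every effort to document progression after symptomatic deterioration. With that schedule kept, last-follow-up censoring is essentially unbiased and last-scan censoring is the rule that drifts low. This stands, and it rules out calling the present rule wrong in all circumstances. It does not close the gaps in step 2, which can occur without any departure from note g.

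A second reply is that last follow-up is undefined and could mean last disease follow-up. That is a fair reading, but the text does not say so.

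Third, events can be recorded without a scan: superficial lesions are measurable with calipers, clinical progression on treatment is recognized in Section 3.7.1, and death from treatment complications counts. This limits the bias but does not remove it for deep or lung lesions.

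A reader might infer that patients are followed by examination alone as a matter of design, or that the 6-month figure is inflated as a matter of fact. The documents support neither. A 90-day median, 30% of patients stopping per scan interval, 120 days of contact after stopping and every post-treatment scan missed would turn 27% into 42%. But the 120 days and the stopping rate appear nowhere in the plan, and missing every scan contradicts note g.

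**Conclusion.** The point holds as a gap in definition with a conditional bias. Section 8.2.1 does not tie censoring to a disease assessment, and the plan leaves room for unscanned follow-up. If note g is followed and no unscanned tail arises, the bias is negligible. With a 30-day unscanned tail the choice of rule moves the 6-month probability by roughly 1 to 6 points, of which about 1 to 4 are upward bias of the present rule. Larger effects need months of follow-up without scans. All sizes rest on the assumed medians and leaving rates. With a 30-day tail the effect is smaller than the sampling error of about 9 points, but it always acts in the favorable direction. The endpoint is secondary and descriptive, and the go/no-go decision on response is untouched. This is a cheap improvement, not a flaw in the trial's main conclusion.

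**What to change.** In Section 8.2.1, replace item (4) with: date of the last evaluable disease assessment (enrollment date if there is none after baseline). Report the analysis censored at last follow-up as a sensitivity analysis. Reconcile Sections 3.5.2 and 3.5.3 with calendar note g, so that post-treatment imaging is stated the same way in each place.

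The cost is one line in 8.2.1, one extra estimate in the report and an editorial reconciliation. Some patients are censored slightly earlier, and those without a post-baseline assessment contribute no follow-up time, so the interval widens. When scan dates vary, the estimate can run up to about 3 points low. Reporting both versions shows how much the censoring date matters.
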